- n For Visit 3, Visit 5, Visit 6, Visit 8, Visit 9, Visit 11, Visit 801, and the ET visit, patients should be reminded to report to the site in a fasting condition, after a period of approximately 8 hours without eating, drinking (except water), or any significant physical activity and before taking their OAMs (if used).
- o Urinary albumin and creatinine will be measured and the ratio will be calculated.
- p The CKD-EPI equation will be used by the central laboratory to compute and report eGFR. Values that are $<30 \text{ mL/min/1.73 m}^2$ at Visit 1 will be required to be retested at Visit 2. If the highest of the 2 values is lower than $<30 \text{ mL/min/1.73 m}^2$ (or lower than the cutoff value for discontinuation of metformin per country-specific label), the patient will be discontinued from the trial prior to randomization. After randomization (Visit 3), values that would require clinical action per protocol or country-specific label must be first confirmed on a retest before any treatment adjustment is implemented.
- q Samples should be collected in P800 tube. Aliquot samples, 1 for glucagon and the remainder for nonpharmacogenetic biomarker.
- r The pharmacogenetic sample should be collected at Visit 3, or at the earliest visit after obtaining local approval.
- s The PK sample should be collected within 30 min after the ECG is obtained on the visits where this procedure is also performed (Visits 6, 9, 11, ET, and 801). At Visit 4, the PK sample can be collected at any time during the clinic visit. The date and time of administration of all dulaglutide doses, and in particular the last dulaglutide dose administered prior to each PK sample, together with the date and time of the PK sample, must be clearly recorded.
- t DID-EQ will be administered at the ET visit only if ET occurs at or before Week 12 (before Visit 6).

3. Introduction

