Two analysis models will be used for the primary and key secondary continuous efficacy measures. The primary analysis will be mixed-model repeated measure (MMRM) analysis using restricted maximum likelihood (REML). The model will include factors for treatment, pooled country, visit, treatment-by-visit interaction and the baseline as a covariate. For analyses of body weight and FSG, the baseline HbA1c stratification ($\geq 8.5\%$ [69 mmol/mol] and $< 8.5\%$) will be added in this model as a fixed effect. An unstructured covariance structure will be used to model

the within-patient errors. If this model fails to converge, the following covariance structures will be tested in order:

- Toeplitz with heterogeneity
- autoregressive with heterogeneity, by visit
- compound symmetry with heterogeneous variances by visit
- Toeplitz
- autoregressive
- compound symmetry without heterogeneous variances, by visit

The first covariance structure that converges will be used.

The secondary analysis for the primary and key secondary continuous endpoints will be analysis of covariance (ANCOVA). Missing endpoints will be imputed with the last (postbaseline) observation carried forward (LOCF) unless otherwise specified. The percentage of patients achieving target HbA1c <7.0% (53 mmol/mol) will be analyzed using a longitudinal logistic regression with repeated measurements.

For continuous measures, summary statistics will include sample size, mean, SD, median, minimum, and maximum for both the actual and change from baseline measurements. Least-squares mean (LS mean) and standard errors (SEs) derived from the model will also be displayed for the change from baseline measurements. Treatment comparisons will be displayed showing the treatment difference LS mean and the 95% CIs for the treatment differences, along with the p-values for the treatment comparisons.

For categorical measures, summary statistics will include sample size, frequency, and percentages. A Fisher's exact test will be used for treatment comparisons.

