5.2. Determination of Sample Size

Assuming a screen failure rate of 40%, approximately 3000 patients will need to be screened to attain approximately 1800 patients randomized to the 3 treatment groups (600 patients/group) in a 1:1:1 ratio for dulaglutide 4.5 mg, 3.0 mg, and 1.5 mg. Assuming 15% dropout rate, this will result in approximately 510 patients per arm completing 36 weeks of treatment (the primary endpoint).

The aforementioned sample size provides $\geq 80\%$ power to demonstrate superiority of at least 1 of the investigational dulaglutide doses (4.5 mg or 3.0 mg) to dulaglutide 1.5 mg with respect to the primary endpoint (change from baseline in HbA1c) at Week 36 (Visit 9). This sample size is calculated based on the assumption that there is a treatment difference (for either investigational dose) in HbA1c change from baseline of approximately -0.22%, a standard deviation (SD) of 1.1%, and a 2-sided alpha of 0.05.

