The efficacy estimand analysis for a longitudinal continuous variable will employ a mixed-model repeated measure (MMRM) using restricted maximum likelihood to obtain model estimates with Kenward-Roger option to estimate denominator degrees of freedom. The model will include factors for treatment, pooled country, visit, treatment-by-visit interaction, and the baseline as a covariate. The observed margins option will be used in the LSMEANS statement whenever this option is allowed. For analyses of body weight and FSG, the baseline HbA1c strata ($\geq 8.5\%$ [69 mmol/mol] and $< 8.5\%$) will be added in this model as a fixed effect. An unstructured covariance structure will be used to model the within-patient errors. If this model fails to converge, the following covariance structures will be tested in order:

- toeplitz with heterogeneity
- autoregressive with heterogeneity, by visit
- compound symmetry with heterogeneous variances, by visit
- toeplitz
- autoregressive
- compound symmetry without heterogeneous variances, by visit
- compound symmetry

The first covariance structure that converges will be used.

The analysis model for nonlongitudinal continuous variables will be analysis of covariance (ANCOVA) coupled with imputation for missing endpoints unless otherwise noted.

For continuous laboratory measurements for safety, an analysis of variance (ANOVA) on ranks on change from baseline using last observation carried forward (LOCF) at Week 36 (Visit 9) and/or Week 52 (Visit 11) will be used with treatment as a fixed effect.

For all continuous measures, summary statistics will include number of patients, mean, SD, median, minimum, and maximum for both the actual and change from baseline values at each scheduled visit for each treatment unless otherwise specified. Least-squares means (LS means) and standard errors derived from the model will also be displayed for the change from baseline values at each scheduled visit for each treatment. Treatment comparisons will be displayed showing the treatment difference LS means and the 95% CIs between each investigational dulaglutide dose and dulaglutide 1.5 mg (treatment differences) at the same visit, along with the corresponding p-values.

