Summary statistics for categorical measures will include number of subjects and percentages. The proportions of patients achieving target HbA1c $<7.0\%$ and $\leq 6.5\%$ at Week 36 (Visit 9) will be analyzed using a longitudinal logistic regression with repeated measurements. In this model, pooled country, treatment, visit, and treatment-by-visit interaction will be fit as fixed effects, and baseline HbA1c as a covariate. A logistic regression model will be applied for the aforementioned HbA1c target analysis at Week 36 (Visit 9) using LOCF by removing visit-related terms from the corresponding longitudinal logistic regression model.

For the analysis of other categorical measures, Fisher's exact test will be used for treatment comparisons unless otherwise specified. Categorical variables will be summarized by sample size and the number of patients and percentages for each treatment group at each visit. Imputed data may be applied in model-based data analyses, but will not be used in data listings. The latter will only present the non-imputed raw data, including site-reported scheduled and unscheduled visits, or early termination visit data; however, only scheduled visits for the measure of interest will be included in the summary table and statistical inference unless otherwise stated.

All statistical analyses will be conducted with SAS Version 9.4® or higher unless otherwise stated.

For primary DBL, all tables, figures, and listings (TFLs) will use the data up to Week 36 (Visit 9) or the study discontinuation date, whichever is earlier, unless otherwise specified.

For the final DBL delivery, TFLs will use the data up to the end of the treatment period (Week 52 [Visit 11]) or the study discontinuation date, whichever is earlier, unless otherwise stated.

Before each DBL, all key data will be reviewed. Any decision to exclude either subjects or observations from the statistical analyses will be made and documented by the study team, and will include the rationale.

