Appendix 1.

Summary of the Data and Primary Analysis for the Primary and Secondary Efficacy Endpoints by Type of Estimand

	Efficacy Estimand	Treatment-Regimen Estimand
Data		
Data Included in the Analyses	
 All patients in the ITT population with a baseline value and at least 1 postbaseline value for the measure of interest are included. Values are excluded after treatment discontinuation or start of antihyperglycemic medications lasting >14 days. 	
 All patients in the ITT population with a baseline value for the measure of interest are included.
Primary Analysis for Each Endpoint		
Primary Endpoint: Change from baseline in HbA1c at Week 36	
 MMRM with effects for treatment, pooled country, visit, treatment-by-visit interaction, and baseline HbA1c as a covariate, 	
 If the Week 36 value is missing, multiple imputation will be used to impute a value such that the reference group includes patients from the same treatment group and same treatment discontinuation status (yes, no) who had a value at Week 36. ANCOVA with effects for treatment, pooled country, and baseline HbA1c as a covariate.
Secondary Endpoint: Change from baseline in body weight at Week 36	
 MMRM with effects for treatment, pooled country, baseline HbA1c stratum (<8.5%, ≥8.5%), visit, treatment-by-visit interaction, and baseline body weight as a covariate. 	
 If the Week 36 value is missing, multiple imputation will be used to impute a value such that the reference group includes patients from the same treatment group and same treatment discontinuation status (yes, no) who had a value at Week 36. ANCOVA with effects for treatment, pooled country, baseline HbA1c stratum (<8.5%, ≥8.5%), and baseline body weight as a covariate.

Summary of the Data and Primary Analysis for the Primary and Secondary Efficacy Endpoints by Type of Estimand

	Efficacy Estimand	Treatment-Regimen Estimand
Primary Analysis for Each Endpoint		

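### The efficacy-estimand MMRM holds the baseline slope equal at all visits, which could cost a little Week 36 precision that a baseline-by-visit term would recover almost free

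*SAP*

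**What the plan says.** The model is stated consistently. SAP 6.1: "The model will include factors for treatment, pooled country, visit, treatment-by-visit interaction, and the baseline as a covariate". SAP Appendix 1, for the primary endpoint: "MMRM with effects for treatment, pooled country, visit, treatment-by-visit interaction, and baseline HbA1c as a covariate". Protocol 10.3.1 gives the same terms: "The model will include factors for treatment, pooled country, visit, treatment-by-visit interaction and the baseline as a covariate". SAP 6.9.2.1.1 carries the structure to body weight and FSG, with the endpoint's own baseline and the HbA1c stratum. On the errors, SAP 6.1 says "An unstructured covariance structure will be used to model the within-patient errors", with simpler structures only if that fails to converge.

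The HbA1c row of the Schedule of Activities marks post-baseline Visits 5, 6, 8 and 9 up to Week 36, that is Weeks 8, 12, 26 and 36. At the primary lock, SAP 6.1 has "all tables, figures, and listings (TFLs) will use the data up to Week 36 (Visit 9) or the study discontinuation date" as the data cut, so four visits enter the model.

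The treatment-regimen estimand is handled differently. SAP 6.9.1.1 uses an ANCOVA on Week 36 alone, whose baseline slope is by construction the Week 36 slope. The point below concerns the efficacy estimand only.

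**The concern.** The model lets the treatment effect differ by visit but not the effect of baseline. There are reasons to expect the baseline effect to change:

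- All arms receive the same doses through Week 8 (protocol 5.1 and 7.1), and protocol 5.4 expects the full HbA1c effect only after about 12 to 24 weeks. Week 8 is therefore an early reading of a response still developing.
- Protocol 5.5 reports larger Phase 2 dose differences in patients with baseline HbA1c of 8.5% or more. If that recurs, it would steepen the average slope at Week 36 in the higher-dose arms. It cannot do so at Week 8, before dosing diverges.
- The subgroup MMRM in SAP 6.12 includes visit-by-subgroup, and baseline HbA1c is one of the subgroups. There the plan does let the baseline effect vary over time.

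If the slope does change, the common slope under-adjusts at Week 36. What is at stake is precision in one of the two primary analyses.

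**Working it through.** **1. The plan's own figure.** SAP 5.2 assumes that "there is a treatment difference (for either investigational dose) in HbA1c change from baseline of approximately -0.22" percentage points, with "a standard deviation (SD) of 1.1%, and a 2-sided alpha of 0.05". It has 600 patients per arm and 15% dropout, so 600 × 0.85 = 510 completers per arm. SAP 6.1.4 splits alpha into 0.025 per dose.

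- SE = 1.1 × √(2/510) = 0.0689, and 0.22/0.0689 = 3.194.
- Power for one dose at 0.05: Φ(3.194 − 1.960) = 89.1%.
- Power for one dose at 0.025: Φ(3.194 − 2.241) = Φ(0.952) = 83.0%.
- Power for at least one dose, both differing by 0.22, correlation 0.5 from the shared control: 1 − Φ₂(−0.952, −0.952; 0.5) = 93.1%.

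The stated power of at least 80% is reproduced.

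**2. What the common slope estimates.** With visit-specific slopes b and residual covariance S, generalised least squares gives

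β = 1′S⁻¹b / 1′S⁻¹1,

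and the Week 36 residual variance becomes S₃₆ + (b₃₆ − β)² × Var(baseline).

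**3. Assumed inputs.** The documents supply none of these. Slopes at Weeks 8, 12, 26 and 36: −0.30, −0.40, −0.52, −0.55 (moderate drift). Baseline SD: 0.7 to 1.0. Week 36 residual SD: 1.0 for the inflation ratio, which is then applied to the plan's SE. The serial correlation is 0.8 per 10 weeks.

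| Assumed residual SD by visit | Weights on the four slopes | β | Gap to −0.55 | SE increase | Per-dose power |
|---|---|---|---|---|---|
| Flat 1.0, equal correlation 0.7 | 0.25, 0.25, 0.25, 0.25 | −0.443 | 0.107 | 0.3–0.6% | 82.7–82.5% |
| Flat 1.0, serial correlation | 0.40, 0.08, 0.10, 0.42 | −0.435 | 0.115 | 0.3–0.7% | 82.7–82.4% |
| 0.75, 0.80, 0.95, 1.0, serial | 0.82, −0.02, −0.03, 0.23 | −0.349 | 0.201 | 1.0–2.0% | 82.2–81.3% |
| 0.55, 0.68, 0.92, 1.0, serial | 1.47, −0.49, −0.08, 0.10 | −0.258 | 0.292 | 2.1–4.2% | 81.3–79.5% |

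Example, last row with baseline SD 0.9: 0.292² × 0.81 = 0.069, so the variance ratio is 1.069 and the SE ratio is √1.069 = 1.034.

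**4. Range.** Over seven assumed covariance structures and baseline SD 0.7 to 1.0:

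- No drift: no loss.
- Small drift (−0.35 to −0.50): SE +0.1% to +2.0%, per-dose power 82.9% to 81.3%.
- Moderate drift (−0.30 to −0.55): SE +0.3% to +5.2%, per-dose power 82.7% to 78.6%. At the worst cell, 3.194/1.052 − 2.241 = 0.794, so power for at least one dose is 1 − Φ₂(−0.794, −0.794; 0.5) = 90.4%.
- Extreme drift (−0.20 to −0.70): SE +1.4% to +17.5%, per-dose power 81.8% to 68.3%. At the worst cell, 3.194/1.175 − 2.241 = 0.477, which gives 83.0% for at least one dose.

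**5. Simulation.** 1,500 trials per scenario, 600 per arm, stratified at 8.5%, about 13% loss at random, unstructured covariance, country omitted, serial correlation, Week 36 residual SD 1.0. Each pair is common slope against baseline-by-visit.

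| Scenario | Mean difference | Model SE | Empirical SD ratio |
|---|---|---|---|
| Flat SD, moderate drift | −0.221 / −0.221 | 0.0606 / 0.0602 (+0.7%) | 1.005 |
| Mild rise, moderate drift | −0.219 / −0.219 | 0.0611 / 0.0602 (+1.6%) | 1.011 |
| Rising SD, moderate drift | −0.218 / −0.218 | 0.0620 / 0.0602 (+3.0%) | 1.013 |
| Rising SD, extreme drift | −0.222 / −0.222 | 0.0665 / 0.0601 (+10.6%) | 1.036 |
| Rising SD, no drift | −0.220 / −0.220 | 0.0601 / 0.0601 | 1.000 |

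The means agree in every row, so no bias appears. The realised loss (last column) is smaller than the rise in model SE.

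**The case against.** The strongest reply is that nothing here is wrong. The model is prespecified, complete and identical in three places, and the alternative is simply another valid specification. The documents contain no evidence that the slope drifts: protocol 5.4 describes when the mean effect is reached, not how change regresses on baseline. Randomization is stratified on HbA1c at 8.5% (SAP 5.3), which limits the imbalance that the slope has to correct. All of this stands, and it is why the point is conditional and small.

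Four stronger readings are tempting and are not supported:

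- *The slope is set mainly by Week 8.* This needs residual variance that rises over visits. That is plausible, since Week 8 is closest to baseline, but the documents do not give it. With flat variance the Week 8 weight is about 0.25 to 0.42, and Week 36 carries about as much.
- *The estimate is biased.* The simulated means agree. Dependence on chance baseline imbalance is the same precision loss described another way.
- *The trial is underpowered.* Per-dose power falls just below 80% only in the least favourable moderate-drift cells, and further under extreme drift. The stated target is at least one dose, with the difference assumed for either dose.
- *The two primary analyses are inconsistent because they adjust differently.* They serve different estimands and by design differ in data, missing-data handling and model.

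**Conclusion.** The constraint is real, and it is avoidable. If the baseline slope changes between Week 8 and Week 36, the Week 36 comparison in the efficacy estimand loses a little precision: about 0% to 5% in SE under small to moderate drift, and nothing if the slope is stable. There is essentially no bias and the test is valid. The target of at least 80% power for at least one dose is still met when both doses differ by 0.22. If only one dose did, the per-dose figures would be the relevant ones, down to 78.6% in the worst moderate cell.

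These sizes rest on assumed slopes, covariances and baseline SD. They apply to HbA1c only: no loss was computed for body weight or FSG, so none should be inferred. This is a free or cheap improvement, not a defect in the primary test.

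**What to change.** Add a baseline HbA1c-by-visit interaction to the HbA1c MMRM in SAP 6.1 and Appendix 1. With four post-baseline visits to Week 36 it adds 4 − 1 = 3 degrees of freedom, negligible with about 1,800 patients.

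The same model is written in protocol 10.3.1, so the change has to be justified in the SAP, and the sponsor should record whether it counts as a principal feature that needs an amendment. It should be made before the primary database lock. After the lock, keep the prespecified model as primary and report the baseline-by-visit version as a sensitivity analysis.

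For consistency the corresponding term can be added for body weight and FSG in SAP 6.9.2.1.1 and Appendix 1, although no gain has been quantified there.

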For continuous laboratory analytes, the change from baseline to endpoint will be analyzed using an analysis of variance (ANOVA) on the rank-transformed data, with treatment as a fixed effect. Last observation carried forward (LOCF) will be used to impute missing postbaseline values. For qualitative laboratory analytes, counts and percentages of patients with normal and abnormal values will be analyzed using Fisher's exact test.

Treatment differences in incidence of hypoglycemic episodes will be assessed by Fisher's exact test. Treatment differences in rates of hypoglycemic episodes may be assessed by a likelihood-based approach for repeated measures with negative binomial distribution if data warrant; otherwise, the Wilcoxon rank-sum test will be used.

2. Schedule of Activities

Visit	Screening and Lead-In		Treatment Period										Safety Follow-Up
	1	2	3	4	5	6	7	8	9	10	11	ET ^a	801
Week of Treatment	-2	-1	1	4	8	12	18	26	36	44	52		56
Allowable Deviation (Days)^b	±3	±3		±3	±3	±3	±7	±7	±7	±7	±7		±7
Informed consent	X												
Randomization ^c			X										
Clinical Assessments													
Medical History (General)	X												
CV risk factor history		X											
Gallbladder disease history		X											
Physical	X												
Height	X												
Weight	X		X	X	X	X	X	X	X	X	X	X	X
Vital Signs (3 sitting BP and PR measurements) ^d	X		X	X	X	X	X	X	X	X	X	X	X
Electrocardiogram	X					X ^e	X		X ^e		X ^e	X ^e	X ^e
Adverse events		X	X	X	X	X	X	X	X	X	X	X	X
Concomitant medications	X	X	X	X	X	X	X	X	X	X	X	X	X
Review/record hypoglycemic events			X	X	X	X	X	X	X	X	X	X	X
Remind patients about 6-point SMPG		X						X		X			
Record 6-point SMPG values ^f			X						X		X	X ^g	
Patient summary											X	X	X
Patient Education and Management													
Dispense study diary, instruct in use		X	X			X	X		X	X	X		
Review study diary			X	X	X	X	X	X	X	X	X	X	X
Return study diary			X			X	X		X	X	X	X	X
Diabetes management education ^h		X											
Dispense PG meter/supplies		X	X	X	X	X	X	X	X	X	X		
PG meter, SMPG training ^h		X	X										
Review SMPG values			X	X	X	X	X	X	X	X	X	X	X
Injection training ^h		X	X										
Dispense study drugs and/or injection supplies			X	X	X	X	X	X	X	X			

Schedule of Activities

Visit	Screening and Lead-In		Treatment Period									Safety Follow-Up	
	1	2	3	4	5	6	7	8	9	10	11	ET ^a	801
Week of Treatment	-2	-1	1	4	8	12	18	26	36	44	52	ET	56
Allowable Deviation (Days) ^b	±3	±3		±3	±3	±3	±7	±7	±7	±7	±7		±7
Patient Education and Management (concluded)													

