Observe patient inject study drug ⁱ			X										
Patient returns study drugs and/or injection supplies				X	X	X	X	X	X	X	X	X	
Assess study drug compliance				X	X	X	X	X	X	X	X	X	
Laboratory Tests													
Serum pregnancy test ^k	X												
Urine pregnancy test ^l			X			X		X			X		
Follicle-stimulating hormone test ^m	X												
Chemistry panel	X								X		X	X	X
Lipid panel (fasting) ⁿ			X						X		X	X	
Urinalysis	X								X		X	X	
Albumin/creatinine ratio (urine) ^o	X								X		X	X	
eGFR (CKD-EPI) ^p	X								X		X	X	X
Cystatin C			X						X		X	X	
Hematology	X								X		X	X	
Immunogenicity			X	X		X			X		X	X	X
Pancreatic amylase, lipase	X		X						X		X	X	X
Calcitonin	X					X			X		X	X	
HbA1c	X		X		X	X		X	X		X	X	X
Glucose (fasting) ⁿ			X		X	X		X	X		X	X	X
Serum insulin (fasting) ⁿ			X						X		X	X	
C-peptide			X						X		X	X	
Plasma glucagon (fasting) ^{n,q}			X						X		X	X	
Pharmacogenetic (stored sample)			X ^r										
Nonpharmacogenetic biomarker (plasma and serum) (stored sample)			X						X		X	X	
PK Samples													
PK samples ^s				X		X			X		X	X	X

Schedule of Activities

Visit	Screening and Lead-In		Treatment Period									Safety Follow-Up	
	1	2	3	4	5	6	7	8	9	10	11	ET ^a	801
Week of Treatment	-2	-1	1	4	8	12	18	26	36	44	52	ET	56
Allowable Deviation (Days) ^b	±3	±3		±3	±3	±3	±7	±7	±7	±7	±7		±7
PRO Questionnaires (Health Economics)													
Diabetes Injection Device Experience Questionnaire (DID-EQ)						X						X ^t	
EQ-5D-5L			X						X		X	X	
Impact of Weight on Self-Perceptions Questionnaire (IW-SP)			X						X		X	X	
Ability to Perform Physical Activities of Daily Living Questionnaire (APPADL)			X						X		X	X	

Abbreviations: BP = blood pressure; CKD-EPI = Chronic Kidney Disease-Epidemiology Collaboration equation; CV = cardiovascular; ECG =

electrocardiogram; eGFR = estimated glomerular filtration rate; ET = early termination; HbA1c = hemoglobin A1c; OAM = oral antihyperglycemic medication; PG = plasma glucose; PK = pharmacokinetic; PR = pulse rate; PRO = Patient-Reported Outcomes; SMPG = self-monitored plasma glucose.

- a Patients who are unable or unwilling to continue in the study for any reason will perform an ET visit. If the patient is discontinuing during an unscheduled visit, that visit should be performed as the ET visit. If the patient is discontinuing during a scheduled visit, that visit should be performed as an ET visit. Visit 801 (Safety Follow-Up Visit) should be performed 4 weeks after the ET visit as the final study visit.

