10.3.4.5. Laboratory Analyses

Laboratory safety measurements will be summarized. For continuous (numeric) laboratory analytes, the change from baseline by visit will be summarized as detailed in Section 10.3.1. Change from baseline to endpoint (LOCF) will be analyzed using an ANOVA on the ranks with treatment as a fixed effect unless otherwise specified. For subjective (qualitative) laboratory analytes, counts and percentages of patients with normal and abnormal values will be analyzed using Fisher's exact test.

Shift tables of the change from baseline value to the most extreme postbaseline value and from baseline to Week 52 for selected analytes using clinically meaningful thresholds will be summarized.

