6.10.4. Clinical Laboratory Evaluation

Analyses of eGFR, creatinine, and UACR are described in Section 6.10.1.2.9. For other laboratory safety parameters, summaries will be provided in this section. For continuous (numeric) laboratory analytes, including serum lipid parameters (total cholesterol, high-density lipoprotein cholesterol, low-density lipoprotein cholesterol, very-low density lipoprotein cholesterol, and triglycerides), the rank of the change from baseline to endpoint (Week 36 [Visit 9] for primary DBL, Week 52 [Visit 11] for final DBL) will be analyzed as detailed in Section 6.1. For qualitative laboratory analytes, the numbers and percentages of patients with normal and abnormal values will be summarized by treatment.

Each pancreatic enzyme (pancreatic amylase [p-amylase] and lipase) and the maximum postbaseline value will be summarized by treatment in a shift table using $>1 \times \text{ULN}$ and $\geq 3 \times \text{ULN}$ separately for the Safety Population, Safety Population with normal baseline value, and Safety Population with baseline value $>1 \times \text{ULN}$.

An MMRM with pooled country, baseline HbA1c strata, treatment, visit, and treatment-by-visit interaction as fixed effects will be fit to analyze each pancreatic enzyme up to Week 52 (Visit 11). In this model, the log-transformed (post first dose measure/baseline measure) will be

the response variable, and log-transformed baseline measure will be used instead of baseline measure. The variance-covariance structure selection is detailed in Section 6.1.

An ANCOVA model for Week 36 (Visit 9) measurement using LOCF will be fit with the same model as the aforementioned MMRM but removing all terms containing visit.

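### As written, the scheduled-visits-only rule in SAP 6.1 leaves Week 36 LOCF nothing to carry for eight of nine safety-laboratory rows and keeps early-termination results out of the extreme-value tables

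*SAP*

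**What the plan says.** SAP 6.1 (General Considerations) describes listings as raw data "including site-reported scheduled and unscheduled visits, or early termination visit data". It then sets a different default for tables and analyses: "only scheduled visits for the measure of interest will be included in the summary table and statistical inference unless otherwise stated". For the primary lock it adds a date limit, under which outputs "will use the data up to Week 36 (Visit 9) or the study discontinuation date, whichever is earlier, unless otherwise specified".

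The safety-laboratory methods are these:

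- SAP 6.1: ANOVA on ranked change from baseline, "using last observation carried forward (LOCF) at Week 36 (Visit 9) and/or Week 52 (Visit 11) will be used".
- SAP 6.10.4, pancreatic enzymes: "An ANCOVA model for Week 36 (Visit 9) measurement using LOCF will be fit", plus a shift table on the highest value after baseline.
- SAP 6.10.4, other analytes: treatment-emergent abnormality tables, and shift tables to the highest value after baseline.
- SAP 6.10.1.2.9: LOCF analyses of renal measures, and a shift table on minimum eGFR and maximum creatinine and urine albumin/creatinine ratio.

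The protocol states the purpose. Its Synopsis (Safety Analyses) says "Last observation carried forward (LOCF) will be used to impute missing postbaseline values" for continuous analytes. Protocol 10.3.4.5 asks for "Shift tables of the change from baseline value to the most extreme postbaseline value".

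**The concern.** The default rule and the planned methods do not fit together. LOCF needs an earlier post-baseline value to carry, and a maximum needs more than one value to choose from. For most safety analytes the only post-baseline sample before Visit 9 that the schedule provides is the ET draw, and the rule sets ET data aside.

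Two things are at stake. First, programmers could reasonably build different Week 36 safety-laboratory tables from the same SAP. Second, patients who leave the study early would drop out of tables meant to show the worst value on study. Protocol 3.2 gives this some weight: in an earlier dose-finding study the monitoring committee recommended stopping the 3.0 mg dose, partly because more patients had pancreatic enzymes above the upper limit of normal. The enzyme shift table in SAP 6.10.4 is where that finding would be re-examined.

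**Working it through.** **Planning figures.** SAP 5.2 and Protocol 10.1 give 600 patients per arm and 15% dropout: 600 × (1 − 0.15) = 510 completers per arm, as stated. The remainder is 600 × 0.15 = 90.

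**Draws in the Schedule of Activities (Protocol 2).**

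| Row | Visits | At Visits 4–8? |
|---|---|---|
| Chemistry | 1, 9, 11, ET, 801 | none |
| eGFR | 1, 9, 11, ET, 801 | none |
| Hematology | 1, 9, 11, ET | none |
| Urinalysis | 1, 9, 11, ET | none |
| Urine albumin/creatinine ratio | 1, 9, 11, ET | none |
| Lipids | 3, 9, 11, ET | none |
| Cystatin C | 3, 9, 11, ET | none |
| "Pancreatic amylase, lipase" | 1, 3, 9, 11, ET, 801 | none |
| Calcitonin | 1, 6, 9, 11, ET | Visit 6 |

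Eight of nine rows have no scheduled post-baseline draw before Visit 9. Visit 3 sits under the Treatment Period heading, but its samples are taken before the first dose (Protocol 5.1). Protocol 10.3.1 defines LOCF as carrying a post-baseline observation, so a Visit 3 value cannot be carried. Urinalysis is partly qualitative; without it the count is seven of eight and the conclusion is the same.

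**Effect on LOCF.** With scheduled visits only, a patient with no Visit 9 sample has no earlier post-baseline value in these eight rows. Week 36 LOCF then adds in effect no patients, and the analysis rests on observed Visit 9 values.

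**Effect on extreme-value tables.** For the same rows, the highest or lowest post-baseline value is one scheduled value at the primary lock (Visit 9) and one of at most two at the final lock (Visits 9 and 11). A patient who leaves before Visit 9 contributes none.

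**A scheduled visit performed as ET.** Protocol 5.1 has a patient who leaves at a scheduled visit perform it as the ET visit. Relabelling that visit as, say, Visit 7 would not bring the sample in, because Visits 4 to 8 are not scheduled visits for these rows.

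**Number affected.** With no sample at Visit 9, per arm: 600 × 0.05 = 30; 600 × 0.10 = 60; 600 × 0.15 = 90. The documents give no ET attendance. If 25%, 50%, 75% or 100% of 90 attended, admitting ET values would regain 22.5, 45, 67.5 or 90 patients, for about 532, 555, 577 or 600 per arm.

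**Illustration only.** Let b be the abnormality rate among patients with a Week 36 sample, L the leavers, n those attending ET, and m the ET rate as a multiple of b. With ET values included, the rate is b × [(600 − L) + n × m] / (600 − L + n). None of b, m or n comes from the documents; b is set at 2%.

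| L, n | m = 0.5 | m = 1 | m = 2 | m = 4 |
|---|---|---|---|---|
| 90, 90 | 1.85% | 2.00% | 2.30% | 2.90% |
| 90, 45 | 1.92% | 2.00% | 2.16% | 2.49% |
| 30, 30 | 1.95% | 2.00% | 2.10% | 2.30% |

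For the first row, the abnormal patients left out number 90 × 0.02 × m = 0.9, 1.8, 3.6 or 7.2 per arm. The count can only fall when ET values are left out, but the percentage can move either way because the denominator falls too.

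**The case against.** The strongest reply is that the literal reading cannot be what the authors meant. The rule is a default that yields to any contrary statement. Naming LOCF and a maximum after baseline could be that statement, since both would otherwise do no work at the primary lock. ET has its own column in the schedule and is marked for all nine rows. The date limit would also let an ET sample in.

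This is plausible as intent, but it does not settle the matter. SAP 6.1 lists ET data beside scheduled visits as a different kind of data and then admits only the latter, and a date limit does not override a rule on visit type. Where the SAP wants more data it says so: adverse events through follow-up (6.10.1), hypoglycemia after new medication (6.10.1.2.2.1), and antibodies through Week 56 (6.10.5). The laboratory sections have no such sentence.

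Other parts of the reply stand:

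- **Unscheduled draws.** Leaving them out is defensible. Samples for suspected pancreatitis are prompted by symptoms, so pooling them could make detection differ between arms. Suspected cases are adjudicated in any event (Protocol 9.2.2.3).
- **Repeat liver tests.** A reader might infer that these are an important loss. A repeat follows an elevation already found, and one taken 3 to 5 days after Visit 9 falls past the primary-lock cut-off.
- **Visit 801.** Whether the study discontinuation date means the ET or the Visit 801 date is undefined for early leavers. That is missing detail, not a contradiction.

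**Conclusion.** The point holds as a minor one. As written, SAP 6.1 excludes collected ET laboratory values from the Week 36 LOCF analyses and from the extreme-value and abnormality tables. For eight of nine rows this conflicts with what the protocol's Synopsis and Section 10.3.4.5 ask for.

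The ceiling is about 90 of 600 patients per arm. It assumes that all of the planned 15% dropout has no Visit 9 sample. The 15% describes patients not completing 36 weeks of treatment, and Protocol 5.1, 7.7.5.4 and 8.2 ask patients who stop drug to stay in the study, so the true number is probably smaller. Of these, only patients with an ET sample can be regained.

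A reader might infer that abnormality rates are understated or that a dose difference is hidden. The documents do not support either: they give no abnormality rates, ET attendance or dropout by arm, so the effect on rates is unknown.

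Not affected in this way are the primary and key secondary results, adverse events, adjudicated events, calcitonin LOCF (it has a Week 12 draw), Week 52 LOCF for patients with a Visit 9 value, and the enzyme MMRM. The excluded values still appear in listings.

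**What to change.** Add one rule to SAP 6.1 and refer to it in 6.10.4 and 6.10.1.2.9:

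1. ET values count as post-baseline values for safety-laboratory LOCF endpoints, and for the maximum/minimum post-baseline shift tables and treatment-emergent abnormality tables. This includes samples from a scheduled visit performed as ET, whether or not the analyte is scheduled there.
2. By-visit summaries and MMRM stay on scheduled visits.
3. Optionally, a supportive version of the extreme-value tables adds unscheduled, symptom-triggered draws. Its drawback is possible unequal testing between arms, so it should stand beside the main version and not replace it.

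It would help to define the study discontinuation date in the same edit. The cost is a few sentences and modest programming; the samples are already collected.
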